#### 1.1.6 Dose Selection

In the pilot trial, events requiring dose reductions were four cases of diarrhea and one case of neutropenia. After dose reduction the majority of patients with diarrhea had their symptoms controlled with over the counter medications. A dose of 400 mg a day has been shown to induce a 82% hematologic response rate in CML and a 57% response rate in GISTs. Once we began to aggressively manage the diarrhea with medication and dose reduction to 400 mg per day, it no longer was a dose limiting toxicity. Based on our clinical experience, the majority of KS patients will tolerate 400 mg a day.

### 1.2 **Biologic/Correlative Studies**

#### 1.2.1 Expression/Activation (phosphorylation) imatinib kinase targets and signaling intermediates.

We will determine by immunohistochemistry the expression and phosphorylation status of PDGF-R in biopsies from baseline and 8 days. In our initial study, we did not anticipate the degree of pathologic regression after 4 weeks of therapy. The marked decrease in KS spindle cells after 4 weeks of therapy not only resulted in the qualitative decrease in the phospho-PDGF-R staining but also resulted in a quantitative decrease in the cell population that was immunoreactive initially. In order to more accurately quantitate the effect of imatinib on the phosphorylation state of our targets we will examine biopsies at an earlier time point. We decided to biopsy patients at 8 days because the  $t_{1/2}$  of imatinib is ~18 hours and the  $t_{1/2}$  of its metabolite, CGP-74588, is ~36 hours and patients should reach steady state concentration after seven days. We have validated phosphospecific antibodies by immunohistochemistry for all of these determinants except c-Kit receptor.

#### 1.2.2 Early Markers of Response

Two to 3 months are often required to determine if a KS patient is responding to a therapeutic agent. If early markers of response could be established that would allow physicians to determine with a degree of confidence which patients were going to respond, then patients who were not going to respond would be free to pursue other treatment options.

Because of the importance of cytokines, angiogenic factors and growth factors produced in KS, a number of recent KS therapeutic trials examined biologic endpoints to determine if they correlated with clinical response. All the studies to date have looked at isolated biologic endpoints based on a priori predictions regarding KS biology and/or the mechanism of action of the drug being studied. In a trial of oral 9-*cis* retinoic acid in KS, soluble Interleukin-6 receptor (sIL6R) was significantly lower at baseline in responders and IL-6 levels increased in responders. In a study of COL-3, a matrix metalloproteinase inhibitor, VEGF levels were shown to decrease in responders while b-FGF remained unchanged. These reports suggest concentrations of cytokines/growth factors at baseline or changes in the concentrations after being on therapy may be used as predictors of response for KS therapies.

Because of the critical role cytokines/chemokines play in KS development, we hypothesize that these growth factors would be useful biologic endpoints that may be predictive of response. In previous studies investigators had chosen two or three biological endpoints to examine. We will perform a proteomics-based screen for biologic endpoints. The reason for this choice is two-fold: 1) This method allows us to simultaneously examine the majority cytokines and chemokines that are implicated in KS development and, 2) We have limited knowledge of which growth factors may be downstream of the PDGF-R and c-kit pathways in KS.

The PerkinElmer Cytokine Chip is designed to analyze the following cytokines from a sample in a multiplexed fashion:

Table 4. Cytokines detected by PerkinElmer Cytokine Chip					
IL-1 alpha	IL-2s Ra	IL-8	IL-17	MCP-1	sTNF RI
IL-1 beta	IL-3	IL-10	EGF	MCP-2	sTNF RII
IL-1ra	IL-4	IL-12p40	ENA-78	MCP-3	TARC
IL-1R4	IL-5	IL-12p70	FGF-basic	MIG	TNF alpha
IL-1s RI	IL-6	IL-13	G-CSF	MIP-1 alpha	TNF beta
IL-1s RII	IL-6s R	IL-15	GM-CSF	MIP-1 beta	VEGF
IL-2	IL-7	IL-16	IFN gamma	MIP-3 alpha	

Included in the kit is a mixture of all cytokines to be used for generating four point standard curves. These are used to estimate the concentration of each cytokine from the samples. After running the assay, slides were imaged using a ScanArray™ Confocal Laser Scanner (PerkinElmer, Cambridge, MA). After imaging, the resulting tif files were quantitated using QuantArray software (PerkinElmer, Cambridge, MA). The data was then exported as an Excel 2000 worksheet and these are collated into a single workbook. An analysis macro was run that subtracts the local background signal from the

signal of each spot. This method adjusts for any differences in background that may occur across an array. The replicate spots are then averaged and tested for outliers using the ESD method (extreme studentized deviate; N=4; Critical Z=1.48). The standards were analyzed by point-to-point linear regression and concentrations of experimental samples were estimated from these standards.

We will examine the cytokine profiles of patients at baseline, 7 days and 28 days to see if there is any correlation between baseline concentrations and clinical response. As noted the standards on the cytokine chip are analyzed by point-to-point linear regression and concentrations of experimental samples are estimated from these standards four-point curve. Thus, the chip should be considered a semi-quantitative assay and all cytokines/chemokines that appear to be potential predictors will be confirmed by ELISA.

#### 1.2.2.1 Receptor Mutation Analysis

Mutations of c-kit and PDGF-R have been shown to play a role in tumorigenesis and imatinib resistance. Activating mutations of c-Kit have been reported in mastocytosis, acute myelogenous leukemia, GISTs, myeloproliferative disorders (MPD) and sinonasal lymphomas. In vitro studies suggest activating mutations in the kinase domain of c-Kit are resistant to inhibition by imatinib. Additionally, activating mutations in the kinase domain of PDGF-R  $\alpha$  have been reported in GISTs. We will correlate the presence or absence of c-Kit and/or PDGF-R mutations with clinical response to imatinib.

As the experience with imatinib therapy for CML increased, it became clear that some patients who initially responded later relapsed. Studies demonstrated multiple mechanisms of resistance including over-expression of BCR/ABL transcripts, acquisition of new chromosomal abnormalities and mutation of the kinase domain. In one study, mutations of the kinase domain appeared to be the mechanism of resistance in 23 of 43 cases. At the time of discontinuation, we will biopsy a lesion that is clearly growing or has not responded and sequence PDGF-R and c-Kit.

If any novel mutations are found in either of these cases, we will determine in vitro whether they are activating mutations and/or resistant to imatinib.

#### 1.2.2.2 Mechanisms of Toxicity

By reducing the dose of imatinib to 400 mg per day, the incidence of AEs should be decreased, but not eliminated.

We hypothesize three potential mechanisms for the increased toxicity of imatinib: 1) antiretrovirals inhibit the metabolism of imatinib resulting in higher concentrations of imatinib compared to those seen in CML and GIST patients; 2) imatinib inhibits the metabolism of antiretrovirals resulting in higher concentrations of antiretrovirals; 3) the increased incidence of diarrhea is related to response of occult GI KS lesions. Our investigations into the effect of HAART on imatinib in the pilot study were inconclusive. Because of the potential inhibition of imatinib by antiretrovirals, we will formally study the pharmacokinetics of imatinib and antiretrovirals during the first 2 weeks of therapy in the first 12 patients. Because this study will have a limited number of patients, and these patients are taking a variety of antiretroviral combinations, we have chosen not to measure the concentrations of antiretrovirals unless we note increased toxicity with normal imatinib levels in this study. If we do see an increase in the plasma level of imatinib, we will attempt to correlate this with specific antiretrovirals or antiretroviral classes. If we find plasma imatinib concentrations to be elevated, we will be able to determine a dose that provides comparable concentrations to those seen in other patient populations, such as CML.

Interestingly, the diarrhea usually occurred 2 to 3 weeks after the initiation of therapy, and its appearance coincided with the onset of clinical response in some patients. This observation led to a third potential explanation of the diarrhea. The patients who had diarrhea may have had occult GI involvement of their KS and the diarrhea was related to regression of the GI lesions. The standard screening for GI involvement of KS is to test the stool for the presence of occult blood. All of the patients enrolled to date have tested negative and were presumed not to have GI involvement. Regressing KS lesions could potentially have a direct irritant effect on the bowel or could produce cytokines locally that lead to diarrhea. To determine if there is GI involvement of KS, we will offer a colonoscopy to all patients who have diarrhea that is not controlled by OTC medication. Some might argue that we should screen all patients with a colonoscopy prior to enrollment, but we feel this would be unjustified at this point since a colonoscopy is not without risk and diarrhea does not occur in all patients. From a practical standpoint, the results of the colonoscopy would have little effect on the conduct of current trial since we would withhold therapy until the

diarrhea abated and then restart at a reduced dose. However, if the diarrhea is correlated with regression of GI lesion, one could justify starting at the same dose level once the diarrhea had abated in future trials.

- 1.2.2.3 Transcription profile of KSHV. Changes in gene expression are a fundamental hallmark of cancer progression and invaluable tool of cancer stages. In the case of KS, KSHV/HHV-8 has been identified as the etiological agent and this assay is designed to identify KSHV genes that might change in response to therapy. We will use reverse-transcription (RT) coupled to amplification using polymerase chain reaction (PCR) to measure the mRNA levels of all KSHV/HHV-8 mRNAs in the tumor. This assay is a research test only and should not be used to make clinical decisions. The purpose of including this assay as part of this trial is to determine its usefulness as a prognostic marker of disease.

### **1.3 Study Design**

The proposed study design will provide clinical response data for imatinib in AIDS-related KS. Additionally the study will allow for investigation of mechanisms of resistance, mechanisms of toxicity as well as potentially developing predictors of response.

Patients will continue on study protocol for 6 months. Treatment will be extended 6 months if the patient has met the criteria for a response or has stable disease. At the end of the 12-month study period, further treatment will be at the discretion of the Investigator. Protocol treatment will be discontinued if the subject develops tumor progression, unacceptable toxicity or develops one of the protocol-defined reasons for treatment discontinuation. In the event of toxicity, patients will have their dose reduced (see Section 5.4-5.6).

Clinical and laboratory evaluations will be performed prior to the initiation of study medications and at Days 1, 8, 15, 29 and every 28 days thereafter.

## **2.0 STUDY OBJECTIVES**

### **2.1 Primary Objectives**

2.1.1 Evaluation of clinical response.

### **2.2 Secondary Objectives**

2.2.1 Evaluation of inhibition of PDGF receptor as determined by immunohistochemistry.

2.2.2 Evaluation of cytokine profiles pre and post imatinib therapy.

2.2.3 Evaluation of pharmacokinetic profile of imatinib and antiretrovirals in HIV patients.

2.2.4 Evaluation of mechanisms of primary and secondary resistance to imatinib therapy.

## **3.0 PATIENT SELECTION**

### **3.1 Inclusion Criteria**

3.1.1 Biopsy proven KS involving the skin, lymph nodes, oral cavity, GI tract and/or lungs. GI and pulmonary involvement must be asymptomatic or minimally symptomatic and not require systemic cytotoxic therapy. At least five measurable, previously non-radiated, cutaneous lesions must be present, which can be used as indicator lesions. Additionally, patient will need three lesions greater or equal to 5 x 5 mm that are accessible for 4 mm punch biopsy.

3.1.2 Serologic documentation of HIV infection at any time prior to study entry, as evidenced by positive ELISA, positive Western Blot, or other federally approved licensed HIV test.

3.1.3 Karnofsky performance status  $\geq$  60% (Appendix IV).

3.1.4 Female patients of child-bearing potential must have a negative pregnancy test within 72 hours before initiation of study drug dosing. Post menopausal women must be amenorrheic for at least 12 months to be considered of non-childbearing potential. Male and female patients of reproductive potential must agree to employ an effective barrier method of birth control throughout the study and for up to 3 months following discontinuation of study drug.

3.1.5 The following lab parameters within 21 days prior to study entry:

- Hemoglobin > 8.0 gm/dL.

- Absolute neutrophil count > 1000 cells/mm^3.
  - Platelet count > 75,000/mm^3.
  - Serum creatinine < 1.5 mg/dL or a measured creatinine clearance of > 60 mL/min.
  - Total bilirubin should be normal. If, however, the elevated bilirubin is felt to be secondary to indinavir or atazanavir therapy, then subjects will be allowed on protocol if total bilirubin < 3.5 mg/dL, provided that the direct bilirubin is normal.
  - AST (SGOT) and ALT (SGPT) < 2.5 times the ULN.
- 3.1.6 Life expectancy of 3 months or more.
- 3.1.7 Age of 18 or older.
- 3.1.8 Ability and willingness to give informed consent.
- 3.1.9 Subjects must, in the opinion of the Investigator, be capable of complying with this protocol.
- 3.1.10 No previous imatinib therapy.
- 3.1.11 Antiretroviral therapy is required for patients except those who have exhausted all available treatment options.

## **3.2 Exclusion Criteria**

- 3.2.1 Concurrent active opportunistic infection (OI).
- 3.2.2 Patient is ≤ 5 years free of another primary malignancy except: if the other primary malignancy is not currently clinically significant or requiring active intervention, or if other primary malignancy is a basal cell skin cancer or a cervical carcinoma in situ. Existence of any other malignant disease is not allowed.
- 3.2.3 Acute treatment for an infection or other serious medical illness within 14 days prior to study entry.
- 3.2.4 Patients may not have had anti-neoplastic treatment for KS (including chemotherapy, radiation therapy, biological therapy, or investigational therapy) within 4 weeks (6 weeks for nitrosourea or mitomycin-C) of study entry.
- 3.2.5 Previous local therapy of any KS indicator lesion within 60 days, unless the lesion has progressed since treatment. Because of the possibility of tattooing, and the difficulty in ascertaining clinically what is active KS versus residual pigment post treatment, any prior

local treatment to the indicator lesions regardless of the elapsed time should not be allowed unless there is evidence of clear-cut progression of said lesion.

- 3.2.6 Patient with Grade III/IV cardiac problems as defined by the New York Heart Association Criteria (e.g., CHF, myocardial infarction within 6 months of study entry) (See Appendix XIV).
- 3.2.7 Female patients who are pregnant or breast-feeding.
- 3.2.8 Patient has another severe and/or life-threatening medical disease.
- 3.2.9 Patient has an acute or known chronic liver disease (e.g., chronic active hepatitis, cirrhosis). Patients with known Hepatitis C infection, but with documentation of no or minimal fibrosis on liver biopsy may be enrolled.
- 3.2.10 Patient has had a major surgery within 2 weeks prior to study entry.
- 3.2.11 Drug-specific exclusion criteria: Coumadin® and systemic corticosteroid treatment, other than replacement doses.
- 3.2.12 Subjects must not have received granulocyte colony stimulating factor within 2 weeks of study entry.

### **3.3 Enrollment Procedures**

This study will be available for enrollment at all AMC sites. Sites must have this protocol approved by their Institutional Review Boards (IRB) and be registered with the AMC Operations Center before they may enroll patients.

After it has been determined that the patient is eligible and an informed consent has been signed by the patient, the patient must be registered on-line via the AMC AdvantageEDCSM Internet Data Entry System. Enrollment and data collection will occur via the AMC Internet Data Entry System.

The participating site will ensure the patient meets all eligibility criteria prior to completing the protocol-specific eligibility checklist. Patients will be enrolled on-line via the AMC Internet Data Entry System no more than one week prior to the initiation of treatment (enrollment one day prior to or on the day of treatment is strongly encouraged). Once the eligibility checklist is submitted a system generated confirmation email will be sent to the enroller upon successful completion of the patient enrollment. If the on-line system is inaccessible, the site should notify the AMC Operations Center (via email at [contact], or by phone at [contact]) for further instructions.

## **4.0 CLINICAL AND LABORATORY EVALUATIONS**

All signs, symptoms, HIV-related and AIDS-defining events (refer to Appendices II and III), death and toxicities must be documented. All signs, symptoms and laboratory results  $\geq$  Grade 2 that are felt to be clinically significant or drug-related, and all HIV-related and AIDS-defining events and deaths must be recorded on the case report forms (CRFs).

All prescription medications taken within 14 days prior to study entry and during the intervals between each visit must be recorded on CRFs. The duration of all anti-HIV medications and all OI treatment and/or prophylaxis medications at the time of enrollment must be recorded in the CRF. All non-prescription medications must be recorded in the clinic record.

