#### **4.4 Final Evaluations/Off Drug, Off Study**

AEs must be reported if the AE began any time within 8 weeks of receiving the study treatment. Additionally, if a site learns of any incidence of death, cancer or fetal anomaly, WHICH IS DRUG RELATED, at any time after the study is closed, the site should notify Novartis. This information may provide additional insight into the safety of Gleevec.

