### 6.1 Classification Of Adverse Events By Severity & Relationship To Study Drug Administration

#### 6.1.1 Adverse Event

Any unfavorable and unintended sign (including an abnormal laboratory finding), symptom or disease temporally associated with the use of a medical treatment or procedure regardless of whether it is considered related to the medical treatment or procedure (attribution of unrelated, unlikely, possible, probable, or definite).

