## 6.3 Adverse Events With Commercial Agents

The AE should be reported on the FDA Form 3500 MedWatch (available from the FDA website at [www.fda.gov/medwatch](http://www.fda.gov/medwatch)). The following AEs should be reported:

- All life-threatening events (Grade 4), which may be due to drug administration.
- All fatal events (Grade 5) while on study (or within 30 days of treatment)
- First occurrence of any previously unknown clinical event (regardless of Grade).

The completed form should be forwarded to:

AMC Operations Center  
The EMMES Corporation  
[name]  
[name]  
[contact]

All AEs, regardless of severity, and whether or not ascribed to study drug administration, will be recorded in the appropriate section of the CRF. Patients withdrawn from the study due to AEs will be followed by the Investigator until the outcome is determined and, when appropriate, additional written reports and documentation will be provided.

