## **8.0 POST-TREATMENT EVALUATION AND EVALUATION AT EARLY DISCONTINUATION OF THERAPY**

Thirty days after discontinuation, a follow-up visit will include: **a complete physical exam including: vitals signs, weight, tumor assessment, Karnofsky performance status (Appendix IV), and toxicity evaluation.**

- At a subject's final study visit, the off-study form will be completed. Permanent discontinuation of drug will be documented.
- Subjects who withdraw for toxicity reasons should be followed until the toxicity resolves/returns to baseline, or at least 1 month, whichever is later. In addition, subjects who go off study for reasons other than toxicity should be followed for at least 1 month after discontinuing drug.

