### 12.2 Statistical Analysis Plan

Summary statistics will be used to describe the study population (such as ranges, medians of age, gender, baseline performance characteristics). The binomial and its exact 95% confidence interval will be used to estimate clinical response rate. A two-sided one-group chi-square test will be performed to detect a 50% response rate. Due to a small sample size, exact logistic regression may be used to evaluate the effect of baseline characteristics and other covariates with the clinical response. To evaluate inhibition of PDGF receptor, we will

correlate the presence or absence of c-kit and or PDGF-R mutations with clinical response to imatinib by performing chi-square tests or Fisher's exact tests. The cytokine/chemokine profile at baseline, 1 week and 4 weeks after of imatinib therapy will be analyzed using the proteomics approach. The concentration of each cytokine from the samples will be estimated. Friedman's test will be used to evaluate changes between time points with respect to cytokine levels. If a significant difference is detected, the Wilcoxon rank sum test will be used for pairwise comparisons. Exact logistic regression analysis will be used to detect any correlation between baseline concentrations and clinical responses. PK parameters including AUC,  $C_{max}$  and elimination half-life of imatinib will be estimated in the first 12 patients. PK parameters including AUC,  $C_{max}$  and elimination half-life of selected antiretrovirals may be estimated in selected patients. Summary statistics will be used to describe PK results. The incidence of specific AEs will be summarized by severity grade. The binomial proportion and its 95% confidence interval will be used to estimate the proportion of patients who experience an AE of severity Grade 3 or higher. The proportions of primary and secondary resistance to imatinib therapy will be estimated. Chi-square tests or Fisher's exact tests will be used to evaluate associations between c-kit and PDGF-R mutations with resistance to imatinib therapy.

Cluster analyses are planned for the real-time QPCR data. To evaluate the associations between single genes and response, categorical data analysis methods are proposed. If feasible, a multivariate model relating gene expression to response will be performed.

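### Sections 4.0 and 6.3 set different minimum rules for entering adverse events on the CRF, so the Grade 3 or higher proportion and the by-grade tables in Section 12.2 can be biased low and can differ by site

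*Combined protocol and SAP*

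**What the plan says.** **Recording.** Section 4.0 first asks that all events be documented, without saying where. Its next sentence gives the CRF rule, which covers signs, symptoms and laboratory values at or above "Grade 2 that are felt to be clinically significant or drug-related, and all HIV-related and AIDS-defining events and deaths must be recorded". There is one grade threshold and one judgement filter, with no separate rule for Grade 3 or 4.

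Section 6.3, under the heading Adverse Events With Commercial Agents, states: "All AEs, regardless of severity, and whether or not ascribed to study drug administration, will be recorded in the appropriate section of the CRF".

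**Definition.** Section 6.1.1 defines an AE as "Any unfavorable and unintended sign (including an abnormal laboratory finding), symptom or disease temporally associated with the use of a medical treatment or procedure", and it does so "regardless of whether it is considered related to the medical treatment or procedure". The items filtered by Section 4.0 are therefore AEs in the sense of Section 6.

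**Analysis.** Section 12.2 will summarise specific AEs by grade and, with a 95% confidence interval, "estimate the proportion of patients who experience an AE of severity Grade 3 or higher". It adds no condition on attribution or clinical importance, and it states no time window.

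**Timing.** Section 4.4 says "AEs must be reported if the AE began any time within 8 weeks of receiving the study treatment". Section 8.0 says "Thirty days after discontinuation, a follow-up visit will include" a physical examination and toxicity evaluation, and it sets minimum follow-up periods of about a month.

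**The concern.** A safety proportion means something only if its numerator is collected in the same way for every patient. Here two sections give different minimum standards for the same events, and neither refers to the other.

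A site could reasonably take Section 4.0 as its working rule. It is the general section on evaluations, whereas the all-AE rule sits under a heading about commercial agents although Section 5.2 has the manufacturer supplying the drug. The trial is open to all consortium sites (Schema and Section 3.3), so practice could differ between them.

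At stake are the Grade 3 or higher proportion, which is the only safety estimate in Section 12.2 given a confidence interval, and the incidence-by-grade tables. Attribution is also hard in this population. Section 1.2.2.2 raises interactions in both directions between imatinib and antiretrovirals, so a site could ascribe an abnormal value to the antiretroviral when imatinib contributed.

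**Working it through.** The plan states no expected rate or precision for this proportion, so there is no figure of its own to reproduce. The check compares the texts, then illustrates the effect with assumed counts.

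**Step 1: which events differ between the rules**

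| Event | Section 4.0 requires CRF entry | Section 6.3 requires CRF entry |
|---|---|---|
| Death, HIV-related or AIDS-defining event | Yes | Yes |
| Grade 2 or higher, judged important or drug-related | Yes | Yes |
| Grade 2, judged neither | No | Yes |
| Grade 3-4, judged neither | No | Yes |
| Other Grade 1 | No | Yes |

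**Step 2: what is caught elsewhere.** SAEs go to the manufacturer whatever the attribution (Sections 6.2 and 6.2.1). Grade 3-5 hospitalisations are reported whatever the attribution (Section 6.1.3). The gap at Grade 3-4 is therefore mainly non-serious events managed without admission, chiefly laboratory values.

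**Step 3: direction.** Let p be the true proportion of patients with at least one Grade 3 or higher AE. Let f be the share of those patients for whom no such event reaches the CRF. A patient leaves the numerator only if all of that patient's Grade 3 or higher events are omitted. Then

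- recorded proportion = p(1 − f)
- bias = −f × p

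The bias cannot be upward. It is zero when f = 0, which is the case if every site follows Section 6.3.

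**Step 4: illustration.** N = 30 is the maximum enrolment in the Schema. It is used here as the denominator by assumption. Neither p nor f is given in the documents. With p = 40% (12 of 30 patients), exact Clopper-Pearson 95% intervals are:

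| Patients not recorded | Recorded | Estimate | 95% CI |
|---|---|---|---|
| 0 | 12/30 | 40.0% | 22.7% to 59.4% |
| 2 | 10/30 | 33.3% | 17.3% to 52.8% |
| 3 | 9/30 | 30.0% | 14.7% to 49.4% |
| 4 | 8/30 | 26.7% | 12.3% to 45.9% |
| 6 | 6/30 | 20.0% | 7.7% to 38.6% |

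The expected bias at p = 40% is −0.10 × 40 = −4 points for f = 10%, −8 for 20%, −12 for 30% and −20 for 50%. Over p from 20% to 60% and f from 10% to 50%, it runs from −0.10 × 20 = −2 points to −0.50 × 60 = −30 points.

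**Step 5: low grades.** Section 4.0 asks for no Grade 1 events beyond the HIV-related and AIDS-defining ones. At a site working to that section, the Grade 1 counts hold little more than what staff chose to enter.

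**The case against.** The strongest reply is that Section 4.0 sets a floor and does not forbid entering more. A site that follows Section 6.3 satisfies both, and a site that omits a Grade 3-4 event breaches Section 6.3. That stands: a reader might infer that the protocol permits such omissions outright, and read as a whole it does not. What remains is that nothing tells a site that the stricter rule governs.

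Second, the filter is narrow. An event must fail both tests, importance and relatedness, to be dropped. Sections 5.4.2 and 5.5.2 require drug to be withheld for several Grade 3-4 findings, and a site could hardly call those unimportant. This stands and limits the likely size.

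Third, the two rules may belong to different CRF pages. Appendix I lists the symptom review and adverse events in separate rows, and CRF instructions come from the Operations Center (Section 11.1). This is possible, but the text does not say so, the definition in Section 6.1.1 spans both, and the instructions are not among the documents.

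Fourth, the illustrated intervals overlap heavily. That is true but does not answer the point. The same patients are counted under both rules, so the shift is a systematic loss and not sampling error.

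A reader might also infer that the safety windows contradict each other: 8 weeks in Section 4.4, and 30 days or a month in Sections 6.3 and 8.0. The documents do not support this. The follow-up periods in Section 8.0 are minimums, and toxicity withdrawals are followed to resolution if that is later. The 30 days in Section 6.3 is a criterion for sending fatal events on a MedWatch form. A reporting period longer than the interval to the last required visit is not a contradiction. What is left is that Section 12.2 names no analysis window.

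**Conclusion.** The two sections set different minimum standards, and the difference reaches Grade 3-4. The Grade 3 or higher proportion and the by-grade tables can be biased low and can vary by site, the tables most clearly at Grade 1. The certainty attaches to the mismatch in wording and to the direction of any bias, not to its size. A reader might take the 2-to-30-point range as an estimate. It is not one, since p and f are both assumed, and the true value is zero if all sites follow Section 6.3.

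The primary response analysis is unaffected. Safety is not among the listed objectives in Section 2, and no decision rule is tied to this proportion. The point should be corrected because the correction is nearly free, but it does not threaten the trial's main conclusion.

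**What to change.** Replace the CRF filter in Section 4.0 with the Section 6.3 rule: every AE, any grade and any attribution, goes on the CRF, with attribution recorded in the categories of Section 6.1.7. A related-only summary can then be produced at analysis without discarding data at entry.

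As a secondary clarification, name the AE analysis window in Section 12.2, consistent with the 8-week reporting period in Section 4.4.

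The cost is a wording change in two sections and more entry of low-grade events, which Section 6.3 already demands. Section 12.1 reports observed drop-out, so patients have already been enrolled. For them, sites should check the clinic record for Grade 3-4 events that were not entered. Section 4.0 requires all events to be documented, so the source information should exist.
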